University of Maryland, Shock Trauma Center Department of Orthopaedics

The Effects of SI Screw Removal on Patient-Reported Pain and Functional Outcomes After Open or Closed Reduction and Internal Fixation of Pelvic Fractures

IRB Number: HP-00063838

NCT02652611

Principal Investigator: [name]

Safety Monitor: [name]

Version 4

August 19, 2022

TABLE OF CONTENTS

Protocol Summary	3
Key Roles	4
Background Information	4
Rationale	5
Potential Risks	5
Potential Benefits	6
Primary Outcome	6
Secondary Outcomes	6
Exploratory Outcomes	6
Description of the Study Design	6
Primary Endpoint	7
Secondary Endpoints	8
Study Population	10
Co-Enrollment Guidelines	11
Recruitment	11
Study Treatments	11
Clinical Evaluation	12
Participant Interviews	13
Study Schedule	13
Assessment of Safety	15
Data Analysis	16
Randomization	17
Data Management	17
Missing Data	18
Research Ethics Approval	18
Informed Consent	19
Vulnerable Populations	20
Participant Confidentiality	20
Study Discontinuation	21
Reports	21
Study Records Retention	21
Supporting Literature	21
APPENDIX A: Study Contacts Roster	23
APPENDIX B: Data Collection Schedule	23

PROTOCOL SUMMARY

Title	The Effect of SI Screw Removal on Patient-Reported Pain and					
	Functional Outcomes After Open or Closed Reduction and Internal					
	Fixation of Pelvic Fractures					
Short Title	SI Screws					
Type of Study	Observational outcomes study and prospective randomized control trial					
	(if applicable based on participant pain at 6-month follow-up)					
Primary Objective	To determine if removing SI Screws 6 – 9 months post SI screw					
	stabilization surgery in pelvic fractures decreases patient reported pain at					
	12 months post SI screw stabilization surgery compared to the SI screws					
	remaining in place					
Secondary Objective	To explore associations between treatment and:					
	1. Patient reported pain up to 24 months post SI screw stabilization					
	surgery					
	2. Narcotic use up to 24 months post SI screw stabilization surgery					
	3. Work productivity & activity impairment up to 24 months post SI screw stabilization surgery					
	4. Health related quality of life up to 24 months post SI screw					
	stabilization surgery					
	5. Pelvic specific functional outcome up to 24 months post SI screw					
	stabilization surgery					
	6. Surgical-related complications					
Sample Size	We will recruit a sample size of 450 observational patients, of which,					
	approximately 150 (75 per arm) will be enrolled in the randomized arm					
	of the study with a 12 month follow-up for the primary outcome					
Diagnosis and Main	Pelvic fracture requiring SI screw placement in patients between the ages					
Inclusion Criteria	of 18 and 80 years of age, inclusive					
Length of Follow-up	24 months					

Study duration: We will recruit for two and a half years. Patients will be followed for 24 months. We estimate 6 years total.

Primary outcome measure: *Patient-reported pain* as measured by using the arithmetic mean of the four pain severity items on the patient-reported Brief Pain Inventory assessment (BPI) 12 months following the patient's injury.

Secondary outcome measures:. Pelvic function will be measured using the Majeed Pelvic Score.

Statistical analysis: We are interested in estimating the causal effect of removal versus non-removal of SI screws in pelvic fracture patients requiring the use of SI screws for stabilization. For all our analyses, we will report estimates of the causal effects, standard errors, and confidence intervals. We will also report the results of tests of null hypothesis of no causal effect.

KEY ROLES

Safety Monitor- [name] will be responsible for overseeing patient safety for the study. [name] will review the enrollment numbers, adverse events, and medical compliance annually for the duration of the study.

Principle & Sub-Investigators- [name] (PI) and the sub-investigators will be responsible for developing a detailed study protocol, providing oversight on study progress and act to correct deficiencies in the conduct of the study. The PI and sub-investigators will also draft the main publications related to the study, and assist with patient consent.

Research Coordinator- [name], research specialists, are responsible for maintaining all study documentation, developing and maintaining the master IRB application and consent, circulating any changes to study documents including protocols, case report forms, and IRB materials to the research team members, providing daily oversight and management of study implementation, performing data quality control and analysis of study results, and conducting monthly reports for the study.

Research Team Members- The research team members are responsible for the conduct of the clinical study including patient enrollment, performing study procedures, data collection and conducting study follow-up visits.

BACKGROUND INFORMATION

Chronic pain following surgical stabilization of a pelvic fracture is very prominent and can have a major effect on a patient's quality of life. Persistent pain after radiographic evidence of fracture union commonly leads to implant removal. But, the routine removal of orthopaedic fixation devices after fracture healing remains an issue of debate. Many surgeons remember patients whose intractable, hardly explainable local symptoms and complaints resolved quickly after the procedure. However, implant removal requires a second surgical procedure in scarred tissue, poses a risk for nerve damage, infection and re-fractures, and is not a guarantee of pain relief.

Rates of implant removal vary based on anatomic location and implant selection. Many studies have introduced and assessed the outcomes of hardware removal in the ankle, tibia and femur. But, there is currently no controlled trial that assesses the benefits and harms of SI screw removal in pelvic fracture patients.

RATIONALE

Reports in literature are not consistent concerning the incidence of painful hardware and the outcome and pain relief after hardware removal. There is conflicting evidence that removing hardware decreases acute pain in ankle, tibia, and femur fractures but there is a need to explore the effect of SI screw removal in pelvic fracture patients. We propose to observe patients requiring SI screw stabilization surgery for 24 months. At 6 months post SI screw stabilization surgery, if the patient reports any pain associated with his/her pelvic injury, they will be asked to enroll in the randomized arm of the study that allows us to prospectively randomize patients to removal versus non-removal of SI screws and track which group has less pain and need for narcotic pain medications.

POTENTIAL RISKS

While the intake questionnaire and information gathered is of a sensitive nature (pain, narcotic use and medical history) and it might cause the patient some discomfort to answer truthfully, all information will be kept confidential and no identifiers will be used in publication.

While every attempt will be made to keep all information confidential and the master link between the patient study number and personal identifiers will be destroyed at the completion of the study, there remains a risk of SI Screws - Protocol v4 (2022.08.19) Page 5 of 24

the potential for the loss/breach of confidentiality. This risk will be minimized by storing all paper questionnaires in a secure, locked location and all electronic data will be password protected.

If the patient enrolled in the randomized arm of the study and is randomized to the screw removal treatment, he/she will be exposed to all of the risks associated with surgery under a general anesthetic including but not limited to: prolonged intubation, heart attack, stroke and death. These risks are extremely rare and will be explained by the anesthesia team, and a separate anesthesia consent will be obtained. The risks of the surgical procedure are rare but include: infection, wound break down, re-fracture, and neurologic injury. A separate surgical consent will be provided to go into more detail of the risks of the procedure.

There may be risks in this study which are not yet known.

POTENTIAL BENEFITS

While there are no direct benefits to patients participating in the study (except for those that may accrue from closer clinical observation as a study patient), participation may help determine the best treatment for pelvic fractures requiring SI screw stabilization in the future. This study also provides a potential benefit of decreased pelvic pain levels.

PRIMARY OBJECTIVE

To compare 12 month assessments of patient reported pain of participants undergoing SI screw removal versus non-removal treatment following a pelvic fracture requiring SI screw stabilization. We hypothesize that there will be a decrease in the Visual Analog Scale (VAS) pain scores in the SI screw removal group as compared to the non-removal group at the patient's 12 month follow-up and beyond.

SECONDARY OBJECTIVES

To compare assessments of narcotic use up to 24 months post SI screw stabilization surgery of participants undergoing SI screw removal versus non-removal treatment following a pelvic fracture requiring SI screw stabilization. We hypothesize that there will be a decrease in the narcotic requirements in the SI screw removal group as compared to the non-removal group throughout the 24 month follow up and beyond.

EXPLORATORY OBJECTIVES

To explore associations between treatment and:

- 1. Work productivity and activity impairment up to 24 months post SI screw stabilization surgery
- 2. Health related quality of life up to 24 months post SI screw stabilization surgery
- 3. Pelvic specific functional outcome up to 24 months post SI screw stabilization surgery
- 4. Surgical-related complications.

DESCRIPTION OF THE STUDY DESIGN

The SI Screw study is an observational study in which patients will be asked to enroll during a clinical

appointment following a pelvic fracture requiring SI screw stabilization surgery. At 6 months post SI screw stabilization surgery, if the patient reports any pain associated with his/her pelvic injury, they will be approached at that time to consent in the randomized arm of the study that allows us to prospectively randomize patients to removal versus non-removal of SI screws. If the patient does not agree to randomization, the patient will continue to be tracked in the observational arm of the study and will choose SI screw removal or non-screw removal treatment for themselves based on personal preference and discussion with his/her surgeon.

A total of 450 patients will be enrolled in the observational arm of the study. Of the 450 observational arm patients, approximately 150 (75 per arm) will be enrolled in the randomized arm of the study. All patients will be recruited from University of Maryland, Shock Trauma Center.

A schematic representation of participant enrollment can be found in the figure below.

Figure: Participant Enrollment

At time of enrollment, participants will be asked to provide basic demographic information, health status and function prior to injury. Study injury characteristics will be obtained from the surgeon and the participant's medical record.

Participants will be prospectively followed at 6 months, 9 months, 12 months, 18 months, and 24 months post SI screw stabilization surgery. All follow-ups will occur in person at the hospital clinic follow-ups or over the phone and will consist of both a clinical examination (when applicable) and interview.

PRIMARY ENDPOINT

The primary endpoint is *patient reported pain severity* as measured by the Brief Pain Inventory assessment (BPI). The BPI is a 15-item questionnaire that assesses the severity of pain, the impact of pain on daily function, the location of pain, pain medications and the amount of pain relief. There is no scoring algorithm but the arithmetic mean of the four severity items can be used as a measure of pain severity and the arithmetic mean of the seven interference items can be used as a measure of pain interference. This assessment has been chosen because it is a short, reliable, patient reported assessment of pain that has been specifically designed for and validated in patients with pain from acute conditions such as postoperative pain.

SECONDARY ENDPOINTS

The secondary endpoints include:

1. *Patient reported pelvic function*. This will be measured using the Majeed Pelvic Score. The Majeed Pelvic Score uses five criteria chosen for functional assessment after major pelvic fractures: pain, standing, sitting, sexual intercourse and performance at work. Each of these clinical parameters is scored, the total being a maximum of 100 points for patients who were working before the injury and 80 points for those who were not. The five sections of the assessment are scored as shown in Table I and discussed below.

Pain. Pain is an important sequel of major pelvic injury, and is given a score of 30 points, allocated according to the six grades listed in Table I. **Standing**. Weight-bearing in the erect position is given 36 points, in three main categories (aids, gait and walking ability), each of which has six grades. **Sitting**. Sitting is an important function in relation to the pelvis, but less so than gait or walking ability. A total score of 10 points is given in four grades. **Sexual intercourse**. For both men and women, four points are allocated for comfort during sexual intercourse. This does not take account of neurological or psychological impotence and is recorded in four grades. If, for any reason, sexual intercourse has not been attempted, a score of four points is given. **Work**. Work performance is allocated 20 points in five grades, ranging from no regular work to return to the same job as before injury with no loss of performance. A patient who was not working at the time of his injury is not scored; his overall assessment is then out of 80 points.

Table I. System for functional assessment after pelvic fractures

Pain - 30 points		Standing - 36 points	
Intense, continuous at rest	0-5	A Walking aids (12)	
Intense with activity	10	-	
Tolerable, but limits activity	15	Bedridden or almost	0-2
With moderate activity, abolished by rest	20	Wheelchair	4
Mild, intermittent, normal activity	25	Two crutches	6
Slight, occasional or no pain	30	Two sticks	8
		One stick	10
Work - 20 points		No sticks	12
No regular work	0-4	B Gait unaided (12)	
Light work	8		
Change of job	12	Connet wells on elmost	0.2
Same job, reduced performance	16	Cannot walk or almost	0-2
Same job, same performance	20	Shuming small steps	4
·····		Gross limp	0
Sitting – 10 points		Moderate limp	10
		Slight limp	10
Painful	0-4	Normal	12
Painful if prolonged or awkward	6		
Uncomfortable	8	C Walking distance (12)	
Free	10		
1100		Bedridden or few metres	0-2
Sexual intercourse - 4 points		Very limited time and distance	4
Sexual intercourse - 4 points		Limited with sticks, difficult without	
Painful	0-1	prolonged standing possible	6
Painful if prolonged or awkward	2	One hour with a stick limited without	8
Uncomfortable	ĩ	One hour without sticks slight pain or limp	10
Free	4	Normal for age and general condition	12

The accumulative grading system is shown in Table II. This gives a breakdown into excellent, good, fair and poor for both working and non-working patients.

Working before injury	Not working before injury	Grade	
>85	>70	Excellent	
70 to 84	55 to 69	Good	
55 to 69	45 to 54	Fair	
< 55	<45	Poor	

Table II. Clinical grade based on a score out of 100 points for working and 80 points for non-working patients (see text)

2. *Surgical-related complications* will be determined by patient medical record review and surgeon recall following follow-up clinic appointments.

STUDY POPULATION

The study population will be patients aged 18-80 with a pelvic fracture that required SI screw stabilization.

Inclusion Criteria:

- 1. The patient is between 18 and 80 years of age, inclusive.
- 2. The patient has a pelvic fracture that required SI screw stabilization.
- 3. The patient has reached skeletal maturity.
- 4. The patient's pelvic fracture is a result of trauma (includes polytraumatized patients).
- 5. The patient is English-speaking.
- 6. The patient's surgeon agrees to randomization (the patient is amendable to either SI screw removal or non-screw removal treatment).
- 7. The patient's pelvic fracture was initially treated at Shock Trauma.

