Patients enrolled in the non-SI screw removal treatment group will not undergo screw removal surgery. If complications arise and/or surgery is required, crossover will be allowed and recorded within study follow-up forms.

CLINICAL EVALUATION

A summary of the clinical evaluations is outlined below and can also be found in Appendix B.

Medical Record Review

At time of consent, information about the participant (medical history, height and weight, etc.) and the participant's injuries and hospital stay will be collected, including mechanism of injury, date and time of injury, presence of and severity of other orthopaedic and non-orthopaedic injuries, procedures done in the hospital, and SI screw surgery characteristics.

Assessment of Study Injuries

The following information will be obtained via medical record review and surgeon recall at the time of enrollment:

- Type of pelvic fracture
- Side of pelvic fracture
- SI joint displacement at time of SI screw stabilization surgery

Assessment of SI Screw Stabilization Surgery

The following information will be obtained via medical record review and surgeon recall at the time of enrollment:

- Type of fracture reduction
- SI screw placement characteristics

- Type of fracture fixation (if applicable)
- Acetabular fracture characteristics (if applicable)

Assessments at 6 months, 9 months, 12 months, 18 months, and 24 months Post SI Screw Stabilization Surgery

- Complications since last follow-up (type, severity, treatment)
- Assessment of fracture healing
- Weight bearing status and ambulation
- Use of ambulatory devices
- Pain assessment
- Narcotic use assessment

X-rays

AP and lateral x-rays at admission, post SI screw stabilization surgery, and at the 6 month, 9 month, 12 month, 18 month, and 24 month follow-ups will be obtained. These x-rays are obtained per standard of care.

PARTICIPANT INTERVIEWS

A summary of the participant interviews performed are outlined below and can also be found in Appendix D.

Enrollment Interview

At the time enrollment, participants will be asked about the following:

- Age, gender, race and ethnicity, and education
- Smoking history
- Previous injuries (specifically pelvis or back)
- Pain medication usage prior to pelvis injury
- Work and health status prior to pelvis injury
- General and pelvic function prior to pelvis injury

Follow-up Interviews

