At 6 months, 9 months, 12 months, 18 months, and 24 months post SI screw stabilization surgery, participants will be asked about the following:

- Any re-hospitalization or outpatient surgery since the last visit for any reason related to his/her pelvic injury
- Rehabilitation received
- Pain medication usage
- Work Status Work Productivity and Activity Impairment
- Pain Brief Pain Inventory
- Health Status VR-12
- Pelvic Function Majeed Pelvic Score

STUDY SCHEDULE

Screening and Consent

All patients between the ages of 18 and 80 (inclusive) with pelvic fracture that required SI screw stabilization surgery will be screened for eligibility by the research coordinator or research team members in close coordination with the surgeon investigators. Screening will typically occur at the time of SI screw stabilization surgery and patients will be tracked until valid enrollment period opens (2 to 8 months post SI screw SI Screws - Protocol v4 (2022.08.19) Page 11 of 24

stabilization surgery). An eligibility checklist form will be completed on every potentially eligible participant and entered onto the electronic data capture system. The treating surgeon will be available via pager to answer questions regarding study eligibility. When the treating surgeon is not available, the study PI will be available to page. Contact information for the PI and alternate contact is available in Appendix A. In most cases, questions should be resolved at this level.

Once eligibility has been confirmed, the informed consent process will be completed by the research coordinator or research team member and attending surgeon. Patients will be approached about potential participation in the study at a standard of care clinic follow-up appointment between 2 and 8 months post SI screw stabilization surgery following determination of eligibility.

Enrollment

Once consented into the study, baseline data regarding participant characteristics, injury characteristics, fracture classification and medical history/co-morbidities will be collected. Characteristics about the hospital course and treatment received will also be collected. A brief interview will be conducted with the participant. All data will be recorded on the paper Case Report Form (CRF) and entered into the electronic data capture system.

Follow-up

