Participants will return for follow-up visits at 6 months, 9 months, 12 months, 18 months, and 24 months post SI screw stabilization surgery. Participants will undergo a clinical evaluation by the treating surgeon and be interviewed by the research coordinator or research team member. These visits tend to mirror clinic visits per standard of care, however there may be some circumstances where patients are unwilling to return to the clinic. In these situations the research coordinator or research team member may obtain as much visit data as possible by phone and/or medical record review to prevent loss of important study information. All data will be recorded on the paper Case Report Form (CRF) and entered into the electronic data capture system.

Retention

Every effort will be made to retain participants in the study. We will keep participants engaged through use of study updates during non-study clinic appointments, and reminder calls/letters for upcoming appointment visit window timeframes.

Visit Windows

Each visit will have an interval of time surrounding the ideal date for the visit during which the visit may be completed and the data included in the trial database. This interval is approximately 2 weeks before or after the ideal date for a visit. Study data will still to be collected even if the visit falls out of the ideal window of time.

ASSESSMENT OF SAFETY

The study will monitor all complications and report adverse events to ensure participant safety. All local IRB requirements for reporting adverse events will be met.

The safety monitor (SM) is responsible for providing medical guidance and overseeing participant safety for the study. The SM participates in determining the course of action necessary to meet safety goals and objectives. This is achieved through the review of complications related or possibly related to study treatment, Serious Adverse Event (SAE) reports; resolving safety issues; and interacting with the Principal and Sub-Investigators at each site.

Reportable New Information (RNI)

The following information must be reported to the IRB within FIVE (5) business days of the investigator becoming aware of the information (please note that a separate RNI must be completed and submitted for each problem/event/report):

- Information that indicates a new or increased risk. For example:

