APPENDIX B: DATA COLLECTION SCHEDULE

Assassment	Enroll-	6	9	12	18	24
	ment	month	month	month	month	month
Stratification Level (AF03)						
SI joint displacement (at time of injury)	Х					
Patient Intake (CRF01)						
Demographics (age, gender, race/ethnicity,	v					
education)	Λ					
Smoking History	Х					
Previous Injuries	Х					
Pre-injury Pain Medication Usage	Х					
Pre-injury Work Status (WPAI:SHP)	Х					
Pre-Injury Health Status (VR-12)	Х					
Pre-Injury Pelvic Function (Majeed Pelvic)	Х					
Index Hospitalization - Clinical Intake (CRF02)						
Date/Time & Mechanism of Injury	Х					
Height & Weight	Х					
Medical History	Х					
Narcotic Use	Х					
SI Screw Surgery Characteristics	Х					
Classification of All Injuries	Х					
Study Injury Characteristics	Х					
Patient Follow-Up (CRF03 & CRF04)						
Brief Pain Inventory (BPI)		Х	Х	Х	Х	Х
Re-hospitalizations or Surgeries		Х	Х	Х	Х	Х
Physical Therapy Tracking		Х	Х	Х	Х	Х
Post-Injury Pain Medication Usage		X	X	X	Х	X
Post-Injury Work Status (WPAI: SHP)		Х	Х	Х	Х	Х
Post-Injury Health Status (VR-12)		Х	Х	Х	Х	Х

Assessment	Enroll-	6	9	12	18	24
Assessment	ment	month	month	month	month	month
Post-Injury Pelvic Function (Majeed Pelvic)		Х	Х	Х	Х	Х
Clinical Follow-Up (CRF05, CRF06, & CRF07)						
Ambulation & Weight Bearing Status		Х	Х	Х	Х	Х
Pain Medication Usage		Х	Х	Х	Х	Х
Fracture Healing Status		Х	Х	Х	Х	Х
Complications (type, severity, treatment)		Х	Х	Х	Х	Х
Treatment SI Screw Removal Surgical			v			
Characteristics (if applicable)			Λ			
Crossover SI Screw Removal Surgical			v	v	v	v
Characteristics (if applicable)			Λ	Λ	Λ	Λ

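### The complications endpoint is taken from records and surgeon recall after clinic visits, so harms may be under-counted in patients followed by phone

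*Combined protocol and SAP*

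**What the plan says.** - **Secondary Endpoints, item 2.** Surgical-related complications "will be determined by patient medical record review and surgeon recall following follow-up clinic appointments". This is the only text that says how the endpoint is determined. Patient report is not named.
- **Description of the Study Design.** "All follow-ups will occur in person at the hospital clinic follow-ups or over the phone", with a clinical examination only where applicable.
- **Study Schedule, Follow-up.** If a patient will not return to clinic, staff "may obtain as much visit data as possible by phone and/or medical record review". The stated purpose is to avoid losing study information.
- **Participant Interviews, Follow-up Interviews.** At 6, 9, 12, 18 and 24 months patients are asked about "Any re-hospitalization or outpatient surgery since the last visit for any reason related to his/her pelvic injury". The list has no question on complications as such.
- **Clinical Evaluation.** Complications since the previous follow-up are listed at the same five time points, with no source given for a phone contact.
- **Appendix B.** The patient-reported item "Re-hospitalizations or Surgeries" is on the patient follow-up forms (CRF03 and CRF04). Complications are on the clinical follow-up forms (CRF05 to CRF07). No text carries the first into the second.

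**The concern.** The Background justifies the trial by the lack of a controlled comparison of the benefits and harms of SI screw removal. Complications are the harm side of that comparison. The endpoint has two named sources, and one of them, surgeon recall after a clinic appointment, adds nothing when the contact was by phone. The other, the medical record, may not show care given at another hospital; the plan does not say whether outside records are sought.

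Potential Risks names infection, wound breakdown, re-fracture and neurologic injury as risks of the removal operation. A wound problem or new numbness managed without admission or surgery would not be brought out by the interview items as listed. A re-admission or operation that the patient does report is collected, but the plan does not say that it counts towards the endpoint.

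Two consequences are possible. Both arms may be under-counted. If the share of phone follow-up also differed between arms, the comparison of harms would partly reflect attendance. Removal patients have an additional operation, which could bring more surgeon contact, but the plan gives no attendance figures by arm.

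**Working it through.** **The plan's own figures.** There is none to reproduce for this endpoint: no complication rate, detection rate, expected phone share or power statement. The only relevant figure is the randomised sample, 2 × 75 = 150, which agrees.

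**What each source yields, by type of contact**

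| Source | Seen in clinic | Phone only | Named for the endpoint? |
|---|---|---|---|
| Surgeon recall after the appointment | Yes | Nothing to recall | Yes |
| Medical record | Yes | Yes; outside hospitals not addressed | Yes |
| Patient-reported re-hospitalisation or surgery (CRF03/04) | Yes | Yes | No |
| Direct question to the patient on complications | Not in the interview list | Not in the interview list | No |

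The exposed events are therefore those in phone-followed patients that were treated elsewhere, or that led to neither admission nor surgery.

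**Illustration of size.** All inputs except the 75 per arm are assumptions.

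- Detection in patients seen in clinic: 0.95
- Detection in patients followed by phone: 0.50
- Phone share *f*: 0.10 in the removal arm; 0.30 or 0.40 in the non-removal arm
- True risk: 8% in both arms, so the true ratio is 1

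Overall detection in an arm = (1 − *f*) × 0.95 + *f* × 0.50.

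- Removal, *f* = 0.10: 0.90 × 0.95 + 0.10 × 0.50 = 0.905, an under-count of 9.5%
- Non-removal, *f* = 0.30: 0.70 × 0.95 + 0.30 × 0.50 = 0.815, an under-count of 18.5%
- Non-removal, *f* = 0.40: 0.60 × 0.95 + 0.40 × 0.50 = 0.770, an under-count of 23%

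Observed risks: 8% × 0.905 = 7.24%, against 8% × 0.815 = 6.52% or 8% × 0.770 = 6.16%.

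Spurious ratio: 0.905 / 0.815 = 1.11, or 0.905 / 0.770 = 1.18. The true risk cancels, so the ratio does not depend on the 8%.

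In events: 75 × 8% = 6 true events per arm. Expected counts are 6 × 0.905 = 5.4 in the removal arm, against 6 × 0.815 = 4.9 or 6 × 0.770 = 4.6 in the non-removal arm. The gap is about 0.5 to 0.8 of one event.

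**Equal phone shares.** At 30% in both arms, detection is 0.815 in each. The ratio is 1.00, and both arms lose 18.5% of events.

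**Wider range.** Assume full detection in clinic, phone detection *s* from 0.3 to 0.8, removal phone share 10%, and non-removal phone share 30% to 50%.

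- Smallest ratio (*s* = 0.8, 30%): (0.90 + 0.10 × 0.8) / (0.70 + 0.30 × 0.8) = 0.98 / 0.94 = 1.04
- Largest ratio (*s* = 0.3, 50%): (0.90 + 0.10 × 0.3) / (0.50 + 0.50 × 0.3) = 0.93 / 0.65 = 1.43

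The model gives each patient one mode of follow-up throughout. A patient phoned at one visit may attend the next, and some events would then be recovered.

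**The case against.** The plan has more protection than the endpoint sentence suggests. Record review is one of the two named sources and needs no clinic visit. The Follow-up text provides for phone contact and record review when a patient does not return, and complications are among the visit data at all five time points. The Missing Data section plans surrogate information for missed clinic visits and sensitivity analyses. Assessment of Safety says that all complications will be monitored and that serious events may be found at unscheduled contacts. Data Management requires complete forms and monthly queries. The visit schedule is the same in both arms, and Exploratory Objectives lists complications last, although the Protocol Summary and Secondary Endpoints treat them as secondary.

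Most of this stands, and it rules out several stronger readings that a reader might infer:

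- *Events in patients not seen in clinic are lost.* Not supported: record review and phone contact can find them.
- *An event reported by phone is excluded.* Not supported: the endpoint sentence does not name patient report, but it does not bar it.
- *A patient followed by phone is scored as free of complications.* No text says so.
- *The arms will be followed differently.* The documents give no phone share, and one extra operation does not establish a difference.

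The safeguards do not close the gap, however. The surrogate information has no stated content and is not tied to this endpoint. Listing complications on a form says where they are written, not how they are found in a patient whom the surgeon has not seen. Nothing says that outside records are sought or that the patient's own report counts.

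**Conclusion.** The point holds as a risk of under-counting, not as a demonstrated loss or a demonstrated bias between arms. The stated rule omits an event source that the trial already collects at every follow-up, and no listed interview item asks about complications that lead to neither admission nor surgery.

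In the illustration the under-count is about 9.5% in the removal arm and 18.5-23% in the non-removal arm, with a spurious ratio of 1.11-1.18. These figures rest wholly on assumed detection rates and phone shares; the ratio bias also requires the phone share to differ by arm. In absolute terms the gap is less than one event. With only about 6 events per arm at the assumed 8% risk, though, the harm estimate is sensitive to single events. The BPI primary endpoint and the sample size are not affected. The change is worth making because it is cheap and the data are largely collected already.

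**What to change.** Amend item 2 of Secondary Endpoints and the interview list as follows.

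1. Determine complications from three sources: the medical record, the clinical follow-up forms (CRF05 to CRF07), and the patient-reported re-hospitalisation and surgery item (CRF03/04) at 6, 9, 12, 18 and 24 months. State that reported events are confirmed from records where possible, including records requested from other hospitals.
2. At every contact, by phone or in clinic, ask patients in both arms the same short questions on the harms named under Potential Risks: infection, wound breakdown, re-fracture and neurologic injury.
3. Record the mode of each visit and report it by arm beside the complication results.
4. Code a visit at which no complication enquiry was made as missing, not as 'none', and handle it under the Missing Data section.

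The cost is a few questions in an existing interview, a visit-mode field, occasional requests for outside records, and possibly a higher reported complication rate. No added visits or change in sample size are needed.
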